10.4 Demographic and Baseline Characteristics

Demographics and baseline characteristics including but not limited to age, gender, body weight, height, body mass index, medical history, and psychiatric history will be tabulated by group using descriptive statistics.

10.5 Endpoint Analysis

10.5.1 Safety Analysis

Safety will be assessed based on reported adverse events, abnormal findings from physical and ophthalmological examination, body weight, vital signs measurements, 12-lead ECGs, C-SSRS score and clinical laboratory assessment results. Additional details will be described in the SAP.

10.5.1.1 Adverse Events

Adverse events will be listed by preferred terms and summarized by system organ class with preferred term based on the MedDRA coding system. The number and percentage of patients who experience one or more AEs will be tabulated. The tabulation will be further classified by severity and relationship to investigational product.

10.5.1.2 Clinical Laboratory Values

Laboratory data from each sampling and changes from baseline will be summarized by descriptive statistics. Laboratory analyses will utilize Visit 3 assessments as baseline values. Parameters will be categorized as low, normal, or high according to the laboratory normal range specifications.

Clinical laboratory outlier criteria will be used to identify values and trends of potential medical importance. A summary for the number and percentage of patients with clinical laboratory outliers for each specified laboratory test will be presented. Similar analyses will be performed for clinically noteworthy changes which would show magnitude of change from baseline.

Criteria for clinical laboratory outliers and clinically noteworthy changes will be described in the SAP.

10.5.1.3 Vital Signs

Vital signs at each measured time point and changes from baseline will be summarized by descriptive statistics.

10.5.1.4 Electrocardiogram

Characteristics of cardiac events at each reading and changes from baseline will be summarized descriptively for interval data (ventricular rate, RR, PR, QRS and QTc) will be calculated for each group. The incidence of abnormalities, based on the clinical interpretations from the investigator, will be enumerated.

QTc as corrected by the Fridericia and Bazett methods will be used as the primary measure of change in QT interval. Changes from baseline for each of the ECG parameters will be summarized using descriptive statistics. Borderline and prolonged QTc will be listed and

frequency table provided. Additionally, the numbers of patients with change from baseline in QTc at appropriate visits categorized as <30 msec, 30 to 60 msec, and >60 msec, will be tabulated and summarized by treatment group as will the number of patients with a QTc interval >500 msec.

10.5.1.5 Ophthalmological Examinations

Any of clinically significant ophthalmological findings as defined in Section 11.3 will be analyzed as adverse events.

The LOCS III grading scores and best corrected visual acuity scores observed during the study will be listed.

Additional details will be described in the SAP.

10.5.1.6 C-SSRS

Any suicidal ideation or behavior on the C-SSRS that develops during the study will be listed. Additional details will be described in the SAP.

10.5.2 Efficacy Analysis

10.5.2.1 Primary Endpoint

To evaluate the efficacy of TS-121 compared to placebo on MDD symptoms in MDD patients, Mixed Model Repeated Measures analysis (MMRM)/non-parametric methods will be used to compare the difference between the three treatment groups on the primary endpoint (change in MADRS score) depending on the distribution of the data. On the primary endpoint (change in MADRS score), as assessed at Week 6, a statistically significant GROUP*TIME interaction effect, with greater reductions in MADRS scores in the TS-121 groups, will be interpreted as indicating efficacy (GROUP: Placebo, TS-121 10 mg and TS-121 50 mg, TIME: Week 2, Week 4 and Week 6).

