3 SYNOPSIS

[figure not shown]
Protocol Title	A Multicenter, Randomized, Double-blind, Placebo-controlled Study of the Safety and Efficacy of TS-121 as an Adjunctive Treatment for Patients with Major Depressive Disorder with an Inadequate Response to Current Antidepressant Treatment
Protocol Number	TS121-US201
Phase of Development	2a
Number of Study Sites	Approximately 25 US sites
Study Drug	TS-121: An oral, investigational new drug with antagonistic activity of the vasopressin 1b receptor (V _{1b} receptor)
Indication	Major Depressive Disorder (MDD)
Number of Patients	
Approximately 180 randomized male and female MDD patients between 18 and 65 years of age inclusive
 
 • Placebo Group: 60 patients • TS-121 10 mg Group: 60 patients • TS-121 50 mg Group: 60 patients
Objectives	
Primary Objectives
 
 • To evaluate the safety and tolerability of TS-121 compared to placebo in MDD patients • To evaluate the efficacy of two dose levels of TS-121 compared to placebo on MDD symptoms in MDD patients 
Exploratory Objective
 
 • To evaluate the effectiveness of biomarkers in predicting TS-121 response with retrospective stratification of patients via baseline values of HPA axis and inflammatory biomarkers
Safety assessments	
Safety and tolerability will be assessed from the time the patient is administered the investigational product through the final study procedure.
 
Safety variables for assessment will include:
 
 • Adverse events • Physical examination • Columbia Suicide Severity Rating Scale (C-SSRS) • Body weight • Vital signs

	
 • Clinical laboratory tests (hematology, biochemistry and urinalysis) • 12-lead electrocardiogram (ECG) • Ophthalmological examinations
Efficacy assessments	
Primary Endpoint
 
 • Change in MADRS total score from Visit 3 (Baseline) to Visit 6 (EOT) 
Secondary Endpoints
 
 • Changes from Visit 3 (Baseline) to Visit 6 (EOT) for CGI-S, SDQ, and HAM-A total scores • Percentage of CGI-I improvers (“Very much improved” or “Much improved”) • Percentage of MADRS responders ($\geq 50\%$ reduction in total score)

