## 6.3.2 Statistical Significance Level

Any statistical test or confidence interval (CI) will be two-sided and will be performed at the 5% level of significance, unless otherwise stated. No adjustment for multiple comparisons will be performed for calculation of CI or statistical significance.

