# Statistical Analysis Plan

Taisho Pharmaceutical R&D Inc.  
Protocol TS121-US201

Statistical Analysis Plan (SAP)

Final 2.0  
18 Dec 2018  
CONFIDENTIAL

Treatment group mean (+/- SE) MADRS total score and total score change from baseline will be plotted versus treatment [Figure 14.2.2.1 and Figure 14.2.2.2].

To evaluate the efficacy of TS-121 compared to placebo on MDD symptoms as measured by the MADRS scale, Mixed Model Repeated Measures analysis (MMRM)/non-parametric methods will be used to compare the difference between the three treatment groups on the primary endpoint (change from baseline in MADRS score) depending on the distribution of the data. The baseline MADRS total score will be included as a covariate. Comparisons of TS-121 10 mg versus placebo and TS-121 50 mg versus placebo will be evaluated at each timepoint.

The following is example SAS programming code that will be used to fit the MMRM model and evaluate treatment mean differences:

```
Proc Mixed Method = REML;  
    Class GROUP Subject_ID VISIT;  
    Model Change = Baseline GROUP VISIT GROUP*VISIT  
        / solution ddfm=kenwardroger;  
    repeated VISIT / sub=Subject_ID type= UN;  
    lsmeans GROUP*VISIT / pdiff alpha=0.05 cl;  
    ods output lsmeans=lsm covparms=cp tests3=t3 diffs=diffs;  
  
run; quit;
```

In case the repeated measures model with unstructured covariance matrix (type = UN) fails to converge then the compound symmetry model (type = CS) will be used.

Least squares treatment group mean differences with 95% confidence intervals will be reported for TS-121 10 mg versus placebo and for TS-121 50 mg versus placebo evaluated at Visits 4, 5, 6/EOT and 7. The primary endpoints for analysis are treatment mean differences at Week 6/EOT [Table 14.2.2.3]. Statistical significance of Type 3 tests and model variance terms will be reported separately [Table 14.2.2.4].

The primary analysis will assess treatment mean differences at Week 6/EOT. An assessment of time on treatment will be performed as an analysis of covariance on the latest assessment of the primary endpoint, change in MADRS score. The model will include all patients in the specified population and may include patients with the baseline assessment and no post-baseline efficacy data. In this model, where TIME will be included as a continuous predictor in this model, a

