# Statistical Analysis Plan

Taisho Pharmaceutical R&D Inc.  
Protocol TS121-US201

Statistical Analysis Plan (SAP)

Final 2.0  
18 Dec 2018  
CONFIDENTIAL

statistically significant GROUP\*TIME interaction effect, with greater reductions in MADRS scores in the TS-121 groups compared to placebo, will be interpreted as indicating efficacy.

The following is example SAS programming code that will be used to fit the analysis of covariance model:

```
Proc Mixed Method = REML;  
    Class GROUP;  
    Model Change = Baseline GROUP TIME GROUP*TIME  
        / solution ddfm=kenwardroger;  
    lsmeans GROUP / pdiff alpha=0.05 cl;  
    ods output lsmeans=lsm2 tests3=t3 solution;  
  
run; quit;
```

Treatment least squares means with 95% confidence intervals will be reported and also slope estimates for the baseline and TIME covariates [Table 14.2.2.5]. Model details will be presented in a statistical appendix.

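### The only written efficacy rule, a GROUP-by-TIME interaction, does not test the Week 6 endpoint, and the protocol and SAP attach it to two different models

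*Protocol*

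**What the plan says.** The protocol Synopsis defines the primary endpoint as the change in MADRS total score from Visit 3 to Visit 6. Protocol 10.5.2.1 analyses that change by MMRM or a non-parametric method. Its rule, introduced as applying to the endpoint at Week 6, is that "a statistically significant GROUP*TIME interaction effect, with greater reductions in MADRS scores in the TS-121 groups, will be interpreted as indicating efficacy". The levels are spelled out as "TIME: Week 2, Week 4 and Week 6".

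SAP 6.3.13.1 fits an MMRM to change from baseline with baseline, group, visit and group-by-visit terms. It reports each dose against placebo at Visits 4, 5, 6/EOT and 7, and states: "The primary analysis will assess treatment mean differences at Week 6/EOT". No sentence says which result on those differences would count as efficacy. The section then adds a second model: "An assessment of time on treatment will be performed as an analysis of covariance on the latest assessment of the primary endpoint". TIME is a continuous predictor there, and a significant GROUP-by-TIME interaction in that model, "with greater reductions in MADRS scores in the TS-121 groups compared to placebo, will be interpreted as indicating efficacy".

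SAP 6.3.2 sets every test at two-sided 5% and adds: "No adjustment for multiple comparisons will be performed for calculation of CI or statistical significance". SAP 6.3.4 notes that no efficacy data are planned at early termination.

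**The concern.** The rule and the endpoint address different hypotheses. Once the response is change from baseline and every TIME level is after baseline, the interaction measures only how the treatment gap moves between visits. A drug that works early and keeps working shows no movement.

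The SAP rule is further from the endpoint. Each patient contributes one record, the latest one, so TIME varies mainly through dropout, missed visits and visit windows. The interaction therefore largely compares early leavers with completers across arms.

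A dose with a clear Week 6 difference could thus miss the only result that either document calls evidence of efficacy. The protocol and SAP versions could also disagree on the same data. What counts as efficacy would then be settled after unblinding.

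**Working it through.** **Inputs from the documents.** 60 patients per arm, 1:1:1 (Synopsis; Protocol 6.2). Two-sided 5% (SAP 6.3.2). Visit windows of ±3 days after Visit 3 (Protocol 9.3). No effect size, SD, correlation or dropout rate is given, and Protocol 10.1 says the sample size is not power-based, so there is no planned figure to reproduce.

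**Assumptions.** SD of change 7, 8.5 and 9.5 at Weeks 2, 4 and 6; between-visit correlation 0.4-0.8, compound symmetry or AR(1); both doses equally effective; complete data for the MMRM calculations.

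**Step 1: what is tested.** Let Δ2, Δ4, Δ6 be a dose's differences from placebo.
- Endpoint null hypothesis: Δ6 = 0.
- Protocol-rule null hypothesis: Δ2 = Δ4 = Δ6 for each dose, with (3−1)×(3−1) = 4 df.

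A constant gap satisfies the second null hypothesis exactly, for any size, SD or correlation. This step needs no assumptions.

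**Step 2: power of the protocol rule.** The noncentrality is λ = n Σ (C d)′(CΣC′)⁻¹(C d), summed over groups. Here d is a group's mean vector minus the average over groups, C takes successive visit differences, and the denominator df are 177. With placebo at 0 and both doses at Δ, the deviations are −2/3, 1/3 and 1/3 of Δ. Their squares sum to 2/3, so λ = 60 × 2/3 × q = 40q, with q = (CΔ)′(CΣC′)⁻¹(CΔ).

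Worked case, compound symmetry, correlation 0.8:
- Var(Week 4 − Week 2) = 49 + 72.25 − 95.2 = 26.05
- Var(Week 6 − Week 4) = 72.25 + 90.25 − 129.2 = 33.3
- Covariance of the two = 64.6 − 72.25 − 53.2 + 47.6 = −13.25
- Determinant = 26.05 × 33.3 − 13.25² = 691.9
- Gap −4/−4/−4: CΔ = (0, 0), so λ = 0 and the rejection rate is 5%.
- Gap −3/−4/−4: CΔ = (−1, 0), so λ = 40 × 33.3/691.9 = 1.93 and power is 16%.
- Gap building linearly to −4: CΔ = (−4/3, −4/3), so λ = 40 × (16/9) × 85.85/691.9 = 8.82 and power is 64%. Here 85.85 = 33.3 + 26.05 + 2 × 13.25.

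Week 6 contrast of one dose with placebo: noncentrality 4/(9.5 × √(2/60)) = 4/1.734 = 2.31, so power is 63%.

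| True gap at Weeks 2/4/6 | Protocol interaction | Week 6 contrast, one dose |
|---|---|---|
| −4/−4/−4 | 5% | 63% (55-73% for SD 10.5 to 8.5) |
| −8/−8/−8 | 5% | over 99% |
| −3/−4/−4 | 8-16% | 63% |
| linear to −4 | 20-64% | 63% |

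The ranges in the interaction column cover all the correlations and both structures.

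A second set of inputs gives the same pattern: SD 8 or 10 at every visit, correlation 0.5 or 0.7, effect 3 or 4 points. A constant benefit gives 5% on the interaction against 38-78% on the Week 6 contrast (normal approximation). A building benefit gives 11-55% against 38-78%. A benefit that is full at Week 2, halved at Week 4 and gone by Week 6 makes the interaction significant in 20-92%, against 5% at Week 6. The direction clause would screen out some of those.

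**Step 3: the SAP rule.** Simulation of the 2-df GROUP-by-TIME F test in the latest-assessment ANCOVA: 6,000 trials per setting, 0-30% dropout after Week 2 or 4 (equal across arms), ±3-day windows, AR(1) 0.7, SD as above or 9 throughout.
- Constant −4 or −8: rejects in 1-5%.
- Linear to −4: 2-9%.
- No effect at all: 1.5-6% in a separate run.
- Constant −4, with 2-5% of patients entered at TIME 0 and change 0: 0.3-2.3%.

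A different simulation used SD 9, compound symmetry 0.6, 10-20% dropout, some patients at TIME 0 and no baseline covariate. It gave 0.9-1.0% (constant −4), 1.4-1.6% (building) and 0.2-0.6% (no effect), against 56-64% for the Week 6 contrast. A constant benefit is hardly distinguishable from no effect.

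**Step 4: side issues for the fix.** Two unadjusted dose tests give 1 − 0.95² = 9.75% for at least one false positive if independent, and 9.1% with the correlation of 0.5 from the shared placebo arm. If Visit 7 is in the SAP MMRM, its GROUP-by-VISIT test has (3−1)×(4−1) = 6 df. A 3- or 4-point gap confined to that off-drug visit makes it significant in 35-98%.

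**The case against.** The strongest reply is that both documents say a significant interaction will be taken as efficacy; neither says that efficacy requires one. The SAP does fix the Week 6/EOT differences as primary, with model, intervals, 5% level and a top-line table (14.2.2.3), and it introduces the ANCOVA only as a look at time on treatment. The protocol sentence also opens by referring to Week 6, so loose drafting is a possible explanation. Both documents call the study a pilot for estimating effect size, and those estimates are safe.

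Much of this stands, but it bears on how serious the problem is rather than whether it exists. A reader still finds one result described as showing efficacy, and it is not the primary contrast. Mentioning Week 6 does not turn an interaction across three visits into a Week 6 test. Efficacy against placebo is a primary objective, and both documents chose to write a rule for it.

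The ANCOVA percentages are fragile. The SAP does not give TIME's unit or say how patients without post-baseline data enter, and the two simulations differ. Only the conclusion of little or no power should be relied on.

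**Conclusion.** The concern holds. That the interaction does not test the Week 6 difference follows from the model alone, and the mismatch between the protocol rule (MMRM, categorical TIME, 4 df) and the SAP rule (latest-assessment ANCOVA, continuous TIME, 2 df) is in the text. The size of the power loss rests on the assumed SDs, correlations, dropout and equal dose effects. The loss is complete for a constant benefit, large for one nearly complete by Week 2, and ranges from large to nil for one that builds linearly. The Week 6 estimates and intervals are unaffected. The declared conclusion is not, so this should be corrected before unblinding.

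**What to change.** Replace the interaction sentence in Protocol 10.5.2.1 and SAP 6.3.13.1 with:

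> Efficacy of each dose is judged by its LS-mean difference from placebo in MADRS change from baseline at Week 6 (Visit 6) from the MMRM, two-sided 5%. The two dose comparisons are not adjusted for multiplicity (SAP 6.3.2); the chance of at least one false positive is about 9%.

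If the sponsor wants error control over both doses, state that rule here instead. Label the MMRM GROUP-by-VISIT test and the ANCOVA GROUP-by-TIME test as descriptive, and add that the former is not evidence of efficacy because VISIT includes off-drug Visit 7. Removing Visit 7 from the model is optional. Bring the restatement of the protocol rule in the SAP's summary of Amendment 4 changes into line.

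SAP Section 1 defines EOT for early discontinuers as their last assessment. State that the MMRM keeps each assessment at its scheduled visit, so that the Week 6 contrast is a Visit 6 contrast.

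The cost is one protocol sentence and one SAP paragraph. The protocol change needs a signed amendment and IRB submission (Protocol 14.1). No new data are needed. The planned LSMEANS statement already outputs the Week 6 contrasts, so no programming changes unless EOT records were to be moved into the Week 6 slot.

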10.5.2.2 Secondary Endpoint

With respect to the secondary outcome variables, the same MMRM/non-parametric methods as described above will also be used to compare the difference between the three treatment groups on the each secondary endpoint depending on the distribution of the data.

Changes from Baseline (Visit 3) to EOT (Visit 6) for the following:

- CGI-S score
- HAM-A total score
- SDQ score

Chi-square test or Fisher's exact test will be used to compare the difference of active treatment groups to placebo group on the following secondary endpoint.

- Percentage of MADRS responders ($\geq 50\%$ reduction in total score)
- Percentage of CGI-I improvers ("Very much improved" or "Much improved")

10.5.3 Pharmacodynamic (PD) Analysis

With respect to the PD outcome variables, the same MMRM/non-parametric methods as described in Section 10.5.2.1 will be used to compare the difference between the three treatment groups on the each of PD endpoint depending on the distribution of the data.

Changes from Baseline (Visit 3) to EOT (Visit 6) for the following:

- Plasma copeptin
- Inflammatory markers (IL-1, IL-6, HS-CRP, and TNF- α)

Pharmacodynamic biomarkers (salivary cortisol, hair cortisol, plasma copeptin, 8h urinary cortisol and inflammatory markers (IL-1, IL-6, HS-CRP, and TNF- α)) will be evaluated post-hoc to explore relationship of responders and non-responders to baseline characteristics. The analysis will be used to inform, potentially, on future trial design. A separate plan will document analyses of PD samples. All results, including baseline PD biomarkers (salivary cortisol, hair cortisol, plasma copeptin, 8h urinary cortisol and inflammatory markers (IL-1, IL-6, HS-CRP, and TNF- α)), will be listed with relevant metadata.

10.5.4 Pharmacokinetic (PK) Analysis

Visit 6 samples will be limited to evaluation of TS-121 PK. The individual plasma concentration of [REDACTED], the last dosing date and time, and actual sampling date and time will be listed. Additional details will be described in the SAP.

10.5.5 Pharmacogenomic (PGx) Analysis

If study results warrants further investigation of genomic variation postulated to be involved in the metabolism, toxicity, pharmacological response, or emerging MDD data to TS-121 or MDD, the sponsor may conduct genetic and other biomedical research on specimens, including genetic analyses (DNA). PGx samples for patients who received TS-121 (including placebo) will be stored for up to 15 years and may be evaluated as information is gained on TS-121 and/or MDD.

11 ADVERSE EVENT REPORTING

11.1 Definitions, Grading & Relationship, Outcome and Follow-up

11.1.1 Definitions

Adverse Event (AE): Any untoward medical occurrence in a patient administered an investigational product, and which does not necessarily have a causal relationship to investigational product. An AE can be any unfavorable or unintended sign (including an abnormal finding), symptom, or disease. AEs include any occurrence that is new in onset or aggravated in severity or frequency from the baseline condition, or abnormal results of diagnostic procedures (including clinically-significant laboratory test abnormalities). Overdose defined in Section 11.6.1 will also be considered as an AE whether or not it is associated with symptoms or abnormal laboratory results.

Events should be considered AEs if they:

- result in discontinuation from the study,
- require treatment or any other therapeutic intervention,
- require further diagnostic evaluation (excluding a repetition of the same procedure to confirm the abnormality),
- are associated with clinical signs or symptoms judged by the investigator to have a significant clinical impact.

Appropriate therapeutic action and follow-up measures will be performed by the investigator in accordance with GCP. These actions and measures will continue until the condition is resolved and/or the etiology is identified. Any non-serious AEs (including laboratory results or other clinical findings) that result in the patient's withdrawal from the study will require the patient to undergo early discontinuation procedures.

Laboratory Abnormalities: It is the responsibility of the investigator to review all laboratory findings for all patients. Abnormal values should be commented upon as to clinical relevance or importance in the study source records or the laboratory report as appropriate. An abnormal laboratory value may be considered an adverse event if the identified laboratory abnormality leads to any type of intervention whether prescribed in the protocol or not. Medical and scientific judgment should be exercised in deciding whether an isolated laboratory abnormality should be classified as an adverse event.

All laboratory abnormalities considered to constitute an adverse event should be reported on the appropriate section of the patient's study source records. Laboratory abnormalities do not need to be listed as separate adverse events if they are considered to be part of a clinical

syndrome that is being reported as an adverse event.

